5 RANDOMIZATION

At the baseline visit (Visit 1, Day 1) patients will be randomized 1:1:1:1 to receive one of three doses of mesdopetam (2.5 mg, 5 mg, or 7.5 mg) or placebo b.i.d. based on the randomization schedule prepared by the unblinded statistician.

During the first week (Day 1 evening dose to Day 9 morning dose) a run-in phase with either 5 mg mesdopetam or placebo b.i.d. will take place, during which all patients allocated to mesdopetam will receive 5 mg mesdopetam b.i.d. and patients allocated to placebo will receive placebo b.i.d. The purpose of the run-in period with 5 mg b.i.d. is to allow for a one-week dose titration for patients randomized to 7.5 mg b.i.d. In a previous Phase 2a study most patients tolerated 5 mg b.i.d. At Visit 2 (Day 9), patients will receive mesdopetam 2.5 mg, 5 mg or 7.5 mg or placebo b.i.d., as randomized.

Randomization will be performed via a web-based Interactive Response System (IRS), using a dynamic balancing (minimization) algorithm. Randomization will be stratified by average (based on at least two valid home diaries) of <6 daily hours and \geq 6 hours of daily ON-time with troublesome dyskinesia at baseline.

During the one-week run-in phase, the IRS will ensure all patients allocated to mesdopetam treatment will receive 5 mg mesdopetam b.i.d., followed by the randomized dose during the treatment period. Patients allocated to placebo will receive placebo during the first week run-in and then continue placebo during the whole treatment period. Any dose reduction will also be managed through the IRS to ensure that blinding is maintained.

6 PLANNED ANALYSES

No statistical analysis plan (SAP) prepared in advance of the data can be definitive and the final Clinical Study Report (CSR) may contain additional tables or statistical tests if warranted by the data obtained. The justification for any such additional analyses will be fully documented in the final CSR.

Worldwide Clinical Trials Controlled Quality Management Document		
WORLDWIDE CLINICAL TRIALS	Sponsor:	Integrative Research Laboratories Sweden AB
	Protocol Number:	IRL790C005
STATISTICAL ANALYSIS PLAN. PHASE 2-3-4		

6.1 Analysis Sets

6.1.1 Safety Analysis Set

The Safety Analysis Set (SAS) will include all randomized patients who received at least 1 dose of IMP. All safety and tolerability evaluations will be presented by the treatment received for the SAS.

6.1.2 Full Analysis Set

The Full Analysis Set (FAS) will include all randomized patients who received at least 1 dose of IMP and who provided at least one valid post baseline diary. All efficacy analyses will be presented by randomized treatment for patients in the FAS.

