10.8. Visit 3 (Day 28 ± 4 days)

The following procedures and assessments are to be carried out at Visit 3:

- Concomitant Medications
- Vital signs (including supine/standing BP)
- Urine pregnancy test (if applicable)
- MDS-UPDRS part 2 (M-EDL) and part 4 questions 4.1 and 4.2
- Modified UDysRS (part 1, 3 and 4)
- Three 24-hour patient home diaries collected
- Three empty 24-hour patient home diaries handed out

Confidential	Version: 5.0	Page 46 of 74
Protocol: IRL790C005	Date: 5 Mar 2021	C C

- Patient motor function review (see Table 3)
- CGI-S
- C-SSRS
- AEs/SAEs
- Dispense IMP
- IMP compliance

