10.14. Early Termination Visits

Patients have the right to withdraw from the trial at any time and for any reason. If a patient discontinues the IMP early, a safety follow-up visit (according to follow-up, Visit 6) should if possible be scheduled within 5-8 days after the last intake of the IMP.

Confidential	Version: 5.0	Page 48 of 74
Protocol: IRL790C005	Date: 5 Mar 2021	5

11.STUDY PROCEDURES / EVALUATIONS

Signed informed consent must be obtained before any screening procedures are initiated. The informed consent procedure is further described in Section 17.

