When instructions appear to have been understood by the patient, a diary concordance session will be initiated during which the patient and the diary trainer/rater will concurrently complete separate training diaries for at least 4 consecutive half-hour intervals (minimum 2 hours). During the diary concordance session, the patient must experience both ON and OFF. The 2-hour session may be extended, as needed, so that the patient experiences OFF. If the patient is OFF at the beginning of the diary concordance session, they may be administered their next dose of levodopa-containing medication in order to experience ON.

When the session is completed, the diary trainer/rater will review and assess the patient's diary concordance with the trainer/rater. The patient is required to reach at least 75% overall diary concordance with the trainer/rater including at least one OFF interval. If the concordance criteria are not achieved, the trainer/rater will schedule a second diary training and diary concordance session within the 8-week screening period and prior start of the baseline diary completion period, unless the patient declines further participation.

Following successful completion of the 24-hour home diary training and diary concordance session, patients will be required to complete 24-hour home diaries on three prespecified days (24-hour periods starting at midnight) prior the baseline visit (Visit 1).

Patients that have not been able to complete at least two valid diaries at baseline (Visit 1) will not be included. Patients not completing at least two valid diaries at Visit 1 may be rescheduled for Visit 1 following additional diary completion training. For diaries completed prior to Visits 3-5, one valid diary is required for each visit for data to be captured. It is important that the Investigator take all possible measure for patients to complete all three of the weekly diaries.

The 24-hour home diaries will be captured on three days during one week at the baseline diary completion period (prior to Visit 1) and Weeks 3, 7, and 11 (i.e. the week's prior Visits 3, 4 and 5). Set dates for the patient to complete diaries are to be agreed in advance. The clinic will call the patient the working day before the first 24-hour registration period, as a reminder, and the working day after the last 24-hour registration period to check for diary completion.

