14.3.2. Full analysis set

The Full Analysis Set (FAS) will include all randomized patients who received at least 1 dose of IMP and who provided at least one post baseline assessment. All efficacy analyses will be presented by allocated treatment for patients in the FAS population.

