6.12 Primary Efficacy Analyses

All applicable statistical tests will be performed at a local significance level consistent with an overall FWER of 5% and the multiple testing strategy described in Section 0. All comparisons between treatments will be reported with 95% confidence intervals (CI) for the difference. All efficacy analyses will be performed by randomized treatment group and adjusted dose group for patients in the FAS, as well as all active doses grouped compared to placebo.

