6.12.1 Estimand

The main study estimand will follow the 'treatment policy' strategy to estimate the treatment effect of mesdopetam (2.5 mg, 5 mg, or 7.5 mg b.i.d.) compared to placebo b.i.d. (treatment) on the

QMD Ref: Worldwide-TMP-ST-005-7.0 Effective: 12Aug2019	Governing QMD: Worldwide-SOP-ST-001
Confidentiality	/ Statement
This document is the property of Worldwide Clinical Trials Inc. and may n prior approval from Worldwide Quality Assurance or in compl	1 1 1
REF: Worldwide-TMP-QA-001f-1.3	Page 27 of 49

Worldwide Clinical Trials Controlled Quality Management Document		
WORLDWIDE CLINICAL TRIALS	Sponsor:	Integrative Research Laboratories Sweden AB
	Protocol Number:	IRL790C005
STATISTICAL ANALYSIS PLAN. PHASE 2-3-4		

change from baseline to Week 12 (population-level summary) in average daily ON-time (hours) (variable) in patients with Parkinson's Disease exhibiting ON-phase dyskinesia, as defined by the inclusion/exclusion criteria (population) regardless of missing motor diary data, any permitted dose reduction, use of amantadine (if any), or discontinuation for any reason.

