6.13 Secondary Efficacy Analyses

All secondary efficacy analyses will be performed on the FAS for all dose levels of mesdopetam (2.5 mg b.i.d., 5.0 mg b.i.d., 7.5 mg b.i.d., and pooled) and placebo.

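### Requiring a valid post-baseline diary for the FAS is an undeclared change that conflicts with the estimand and keeps the earliest leavers out of the missing-data sensitivity and responder analyses

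*SAP*

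**What the plan says.** **Analysis set.** SAP 6.1.2 admits randomised patients with at least one dose "who provided at least one valid post baseline diary". Protocol 14.3.2 has the same structure but asks for patients "who provided at least one post baseline assessment", without saying what kind of assessment. SAP Section 9 lists 14 departures from the protocol, including the new PK set and CYP subset, but not this one.

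**Estimand.** SAP 6.12.1 adopts a treatment-policy strategy "regardless of missing motor diary data, any permitted dose reduction, use of amantadine (if any), or discontinuation for any reason".

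**Where the FAS applies.** SAP 6.12 states: "All efficacy analyses will be performed by randomized treatment group and adjusted dose group for patients in the FAS". SAP 6.13 adds: "All secondary efficacy analyses will be performed on the FAS". SAP 6.14 says the same of the exploratory analyses, which include the responder analysis. The control-based imputation (SAP 6.12.4.1) feeds the same MMRM as the primary.

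**When efficacy data arise.** Protocol 11.2.3.1 places the on-treatment diaries in "Weeks 3, 7, and 11 (i.e. the week's prior Visits 3, 4 and 5"). The key secondaries are first rated on treatment at Visit 3, where Protocol 10.8 lists "MDS-UPDRS part 2 (M-EDL) and part 4 questions 4.1 and 4.2" together with the modified UDysRS. For early IMP discontinuation, Protocol 10.14 says that "a safety follow-up visit (according to follow-up, Visit 6) should if possible be scheduled within 5-8 days after the last intake of the IMP". Visit 6 (Protocol 10.13) has no diary, MDS-UPDRS or UDysRS.

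**Responders.** SAP 6.2.15 classes anyone withdrawn before Week 12, or with no Week 12 data, as a non-responder.

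**The concern.** The estimand is meant to hold whatever happens to a patient's diaries or treatment, yet having a valid diary decides whether the patient is analysed at all. A patient who leaves before the diary week ahead of Visit 3 has no scheduled route into the FAS. SAP 6.2.3 expects such patients: it sets separate withdrawal windows for the run-in and for the time from run-in to Visit 3.

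The control-based imputation and the tipping point are there to show how far the result depends on assumptions about patients who leave. If the earliest leavers are outside the set, the unfavourable assumption reaches fewer patients and the result can look more robust than it is. The responder analysis has the same gap: its rule makes withdrawals failures, but these withdrawals disappear from the denominator.

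**Working it through.** **1. The plan's own figure.** SAP Section 4 gives a 3 h difference, SD 3.5 h, 31 evaluable per group and 92% power; Protocol 14.2 gives two-sided alpha 0.05. Normal approximation: 3 / (3.5 × √(2/31)) = 3.37; 3.37 − 1.96 = 1.41; power 92.1% (noncentral t: 91.3%). The figure reproduces and is not at issue.

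**2. What each analysis does with a patient who has no post-baseline diary.**

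| Analysis | Protocol FAS (any assessment) | SAP FAS |
|---|---|---|
| Primary MMRM (SAP 6.12.3: MAR, no imputation) | No change score, contributes nothing | Excluded; same estimate |
| Control-based imputation (6.12.4.1) | Could be imputed | Excluded |
| Tipping point (6.12.4.2) | Could be imputed and shifted | Excluded |
| Responder analysis (6.2.15, 6.14.3) | Non-responder | Out of the denominator |
| Key secondaries, left before Visit 3 | No post-baseline rating | Excluded; same estimate |
| Key secondaries, rated at Visit 3 or later, no valid diary at any visit | Included | Excluded |

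Imputation is feasible: inclusion criterion 8 requires two valid diaries at Visit 1, and the PROC MI code in SAP 6.12.4.1 already uses the baseline value.

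**3. Size in the control-based analysis.** The documents give no early-leaver rate, so let e be the assumed fraction of an active arm that leaves before a first diary. Under the control-based rule those patients take, on average, the placebo mean (assuming baselines similar to those of the other patients). Ignoring later dropout:

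- effect with early leavers restored = 3.0 × (1 − e)
- effect in the FAS only = 3.0

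With about 38 per arm (154 / 4 = 38.5) and an illustrative 50% FAS responder rate, the rate in all treated patients is 50% × (1 − e):

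| e | Patients per arm of 38 | Restored effect | FAS-only effect | Responder rate, all treated |
|---|---|---|---|---|
| 5% | 1.9 | 2.85 h | 3.0 h | 47.5% |
| 10% | 3.8 | 2.70 h | 3.0 h | 45.0% |
| 15% | 5.7 | 2.55 h | 3.0 h | 42.5% |
| 20% | 7.6 | 2.40 h | 3.0 h | 40.0% |

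A simulation with 12% of active and 5% of placebo patients leaving early gave 3.0 h for the FAS only and 2.65 h with early leavers restored, against 3.0 × 0.88 = 2.64 h by formula.

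**4. Tipping point.** If early leavers sit δ hours below placebo, the effect is 3.0 × (1 − e) − e × δ. At δ = 2 h this is 2.85 − 0.10 = 2.75 h for e = 5%, and 2.55 − 0.30 = 2.25 h for e = 15%. SAP 6.12.4.2 also describes subtracting δ from MAR-imputed values. If those values equal the arm's own mean, the effect is 3.0 − e × δ: 2.90 h and 2.70 h. In the FAS-only version these patients contribute no shift on either reading.

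**5. Evidence on early exit.** Protocol 4.6 reports discontinuation for AEs in the 28-day Phase 2a study of 2/39 (5.1%) on mesdopetam and 1/36 (2.8%) on placebo. In Phase 1b it was 2/11 on mesdopetam, and all 4 placebo patients completed. SAP Section 4 says that dropout, checked once 70 patients had completed Visit 3, was higher than expected; it gives no rate, timing or arm.

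**The case against.** The strongest reply is that the FAS wording changes no primary result. That is right. A reader might infer that the diary condition biases the primary estimate, but the MMRM uses observed change scores without imputation, so the protocol's FAS would give the same answer. These patients are missing from the primary because of the observed-data model and because no efficacy data are collected after early discontinuation.

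A reader might also infer that early leavers are lost from the key secondaries through this wording. They are not: Q4.2 and UDysRS are first rated on treatment at Visit 3, so such patients have no post-baseline value under either definition. The condition removes only patients rated in clinic who have no valid diary at any of Visits 3 to 5. One valid diary out of nine is enough to qualify, and patients are trained and reminded, so this group is probably very small.

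Three further limits stand. A patient leaving during the diary week may already have a valid diary, so not everyone who leaves before Week 4 is lost. The protocol's term is open: if it meant an efficacy assessment, early leavers were already outside the set, and the SAP mostly makes that explicit. Numbers in each set and early terminations with reasons will be tabulated by arm (SAP 6.4), so the exclusions will be visible.

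Visibility does not put these patients into the analyses designed to test dropout. Nor does the ambiguity in the protocol reconcile the FAS with the estimand.

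**Conclusion.** The concern holds for the population of the sensitivity and responder analyses, and for the undeclared change in wording. The diary condition conflicts with the stated estimand, keeps patients without a first post-baseline diary out of the control-based imputation and the tipping point, and undercuts the SAP's own non-responder rule. A small effect on the clinic-rated key secondaries is also possible.

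If 5–20% of an active arm left before a first diary, a 3.0 h control-based effect would become 2.85–2.40 h. This rests on an assumed leaver rate, on the placebo mean for early leavers and on ignoring later dropout. Phase 2a points to the lower end.

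A reader might conclude that the exclusion favours mesdopetam. That needs more early dropout on active drug than on placebo. It is plausible, since parkinsonism during titration was the commonest Phase 2a AE, but it is not shown: the earlier counts are small and no arm-level figure for this trial is given. The point is worth correcting before unblinding, but it does not undermine the primary estimate or the power calculation.

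**What to change.** 1. Run the control-based imputation, the tipping point and the responder analysis on all randomised, treated patients with a baseline diary. The primary MMRM needs no change.
2. Analyse each clinic-rated endpoint on all treated patients with a post-baseline value of that scale, without a diary condition.
3. List the FAS wording in SAP Section 9 as a change from Protocol 14.3.2, with the reason.

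The cost is SAP text and a few more patients in the imputation. The sensitivity and responder results may be slightly less favourable. For scale, take 38 per arm, e in both arms, and power = Φ(Δ / (SD × √(2/n)) − 1.96). At e = 10%, approximate power of the control-based comparison is 94% on the FAS only (Δ = 3.0, SD = 3.5, n = 34.2). On the restored set (Δ = 2.7) it is 89% if imputed patients add no information (SD = 3.5, n = 34.2), and 91% if they count in full (n = 38, SD widened to 3.56 for the mixture).

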6.1.3 Per Protocol Set

The Per Protocol Set (PPS) will consist of patients from the FAS without protocol deviations that impact the efficacy assessment. Situations which impact the efficacy assessment may include (but are not limited to) those patients who:

- Did not satisfy all of the inclusion/exclusion criteria
- Any patients with treatment administration errors
- Any patients taking inadmissible concomitant medications

Patients who are to be included or excluded from the PPS will be identified and listed following a Blind Data Review (BDR) performed prior to the conclusion of the clinical investigation, database lock and unblinding. Any deviation considered to have a serious impact on the efficacy results will lead to the relevant patient being excluded from the PPS. Any patient exclusions from PPS will be documented in a patient evaluability document before database lock.

6.1.4 Pharmacokinetic Analysis Set

The Pharmacokinetic (PK) Analysis Set will include all randomized patients who received at least 1 dose of IMP and who have at least one evaluable PK concentration data.

QMD Ref: Worldwide-TMP-ST-005-7.0 Effective: 12Aug2019	Governing QMD: Worldwide-SOP-ST-001	
Confidentiality Statement		
This document is the property of Worldwide Clinical Trials Inc. and may not be duplicated, copied, altered or removed from company without prior approval from Worldwide Quality Assurance or in compliance with Worldwide Standard Operating Procedures.		
REF: Worldwide-TMP-QA-001f-1.3	Page 13 of 49	

Worldwide Clinical Trials Controlled Quality Management Document		
WORLDWIDE CLINICAL TRIALS	Sponsor:	Integrative Research Laboratories Sweden AB
	Protocol Number:	IRL790C005
STATISTICAL ANALYSIS PLAN. PHASE 2-3-4		

6.1.4.1 CYP Genotype Subset

The CYP Genotype Subset will be a subset of the PK Analysis Set including patients who consented to genotyping with respect to CYP2D6 and who received a genotype classification result.

6.2 Derived Data

This section describes the derivations required for statistical analysis. Unless otherwise stated, variables derived in the source data will not be re-calculated.

6.2.1 Race

Where more than one race category has been selected for a patient, these race categories will be combined into a single category labelled "Multiple Race" in the summary tables. The listings will reflect the original selected categories.

6.2.2 Baseline

Baseline is defined as the last non-missing value (either scheduled, unscheduled or repeat) before the patient receives the first dose of study drug.

6.2.3 Early Withdrawal Assessments

Early withdrawal assessments will be summarized as a separate visit and will be mapped to an expected visit window as follows:

- During the run-in period
- Post run-in and prior to visit 3
- At visit 3 or post visit 3

6.2.4 Duration / Study Day / Time

Study day will be calculated as the number of days from first dose of study drug.

- date of event date of first dose of study drug + 1, for events on or after first dose
- date of event date of first dose of study drug, for events before first dose

QMD Ref: Worldwide-TMP-ST-005-7.0 Effective: 12Aug2019	Governing QMD: Worldwide-SOP-ST-001	
Confidentiality Statement		
This document is the property of Worldwide Clinical Trials Inc. and may not be duplicated, copied, altered or removed from company without prior approval from Worldwide Quality Assurance or in compliance with Worldwide Standard Operating Procedures.		
REF: Worldwide-TMP-QA-001f-1.3	Page 14 of 49	

6.2.5 Conventions for Missing and Partial Dates

All rules explained below for partial / missing dates will be followed unless contradicted by any other data recorded on the electronic Case Report Form (eCRF).

All dates presented in the individual patient listings will be as recorded on the eCRF (i.e., not completed as per the below rules).

Missing and partial start and stop dates will be imputed to identify treatment-emergent AEs and concomitant medications as follows.

Partial or missing stop date will be imputed as follows:

- If the stop date is completely missing and the event has resolved, or the patient has stopped taking the concomitant medication, the stop date will be imputed as the date of the patient's last clinic visit in the study.
- If only the year is known, the stop date will be imputed as "31-Dec" of that year or as the date of the patient's last clinic visit in the study if in the same year.
- If the month and year are known, the stop date will be imputed as the last day of that month unless the stop date corresponds to the same month as the patient's last clinic visit in which case the date of patient's last clinic visit in the study will be used instead.

Missing start date will be imputed as follows:

- If the stop date occurs on or after the start of study drug or the event / concomitant medication is ongoing, the start date will be imputed as the date of the first dose of study drug.
- If the stop date occurs before the start of study drug, the start date of the event / concomitant medication will be imputed as the patient's screening date or the stop date of the event / concomitant medication whichever the earlier.

Partial start date (year present, but month and day missing)

- If the stop date occurs on or after the start of study drug or the event / concomitant • medication is ongoing, and the year is the same as the year of first dosing the start date will be imputed as the date of the first dose of study drug. If the year is different from the year of first dosing "01-Jan" will be used.
- If the stop date occurs before the start of study drug, the start date of the event / concomitant • medication will be imputed as the "01-Jan" of the same year.

Partial start date (month and year present, but day missing)

QMD Ref: Worldwide-TMP-ST-005-7.0 Effective: 12Aug2019	Governing QMD: Worldwide-SOP-ST-001	
Confidentiality Statement		
This document is the property of Worldwide Clinical Trials Inc. and may not be duplicated, copied, altered or removed from company without prior approval from Worldwide Quality Assurance or in compliance with Worldwide Standard Operating Procedures.		
REF: Worldwide-TMP-QA-001f-1.3	Page 15 of 49	

Worldwide Clinical Trials Controlled Quality Management Document		
WORLDWIDE CLINICAL TRIALS	Sponsor:	Integrative Research Laboratories Sweden AB
	Protocol Number:	IRL790C005
STATISTICAL ANALYSIS PLAN. PHASE 2-3-4		

- If the stop date occurs on or after the start of study drug or the event / concomitant medication is ongoing, the start date will be imputed as the first day of the same month and year unless this partial start date is in same month as the first dose of study drug in which case the date of first dose of study drug will be used.
- If the stop date occurs before the start of study drug, the start date will be imputed as the first day of the month and year of the partial stop date.

If the start time is missing it will be imputed only in the case where the start date of the concomitant medication / event corresponds to the date of the first dose of study drug. The time will be imputed as the same time as the first dose of study drug. In all other cases the time will not be imputed.

